In a four-session within-subjects study we will compare a placebo control to 300, 600 and 900mg of cannabidiol. In Aim 1 we will explore how cannabidiol affects reactions to rewarding vs. aversive pictures. Participants will view pleasant pictures (e.g. of parties, pets, sunsets), neutral pictures (e.g. of household objects, neutral landscapes) and unpleasant pictures (e.g. medical imagery, war scenes and disgusting objects) drawn from the standardized International Affective Picture Set (IAPS) while we measure subjective responses to these pictures using self-reports. We predict that cannabidiol will reduce subjective and psychophysiological responses to negative pictures without affecting responses to positive pictures. In Aim 2 we will examine responses to emotional facial expressions, which are an ecologically relevant category of rewarding and aversive stimuli. We will measure how quickly individuals are able to perceive happy vs. negative facial expressions using dynamically developing expressions of happiness, fear, anger and sadness. We predict that cannabidiol will blunt perception of, psychophysiological responses to and attentional bias towards negative facial expressions without affecting responses to positive facial expressions. In Aim 3 we will examine the relationship of responses to emotional stimuli with talkativeness in a controlled social interaction. We predict that cannabidiol will increase talkativeness, and this effect will be mediated by the decreased responses to negative social and emotional stimuli measured in the previous aims. Finally, on an exploratory basis we will measure the subjective effects of cannabidiol, and specifically the its effects on anxiety, sedation and euphoria, with the aim of determining whether CBD's effects on responses to emotional stimuli are related to, or independent of, its subjective effects.

Methods:

Design: The study will use a 4-session within-subjects double-blind design in which participants will receive three doses (300, 600mg and 900mg oral) of cannabidiol and a placebo in randomized order. All screening, orientation, and study session procedures

will take place in the Human Behavioral Pharmacology Laboratory suite in the L4 wing of [name]

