Subjects: We will recruit 50 healthy volunteers, with the expectation (based on previous retention rates) that 36 healthy volunteers (18 male, 18 female; age range 18-35 years) will complete all experimental procedures. All participants will be recruited without regard to race, religion or ethnicity through posters, advertisements and word-of-mouth referrals. Candidates will be screened in accordance with our general screening protocol, approved by the IRB under Protocol #13681B, which includes a physical, EKG, psychiatric screening interview and detailed drug use history questionnaire. Because CBD will be administered as part of the study, the following populations are excluded for safety reasons: Individuals with a medical condition contraindicating study participation, as determined by our physician, individuals regularly using any medications aside from hormonal contraception in women, individuals with a current (active in the past year) DSM-IV Axis I mood, anxiety, eating, or substance dependence disorder or a lifetime history of a psychotic disorder or mania; women who are pregnant, nursing, or planning to become pregnant in the next 3 months; anyone reporting a known or suspected allergy to cannabinoids. The self-report questionnaires we use require fluency in English, and have not been translated and validated in other languages, thus individuals with less than a high-school education or those not fluent in English will be excluded, as lack of English familiarity at a high school level may compromise our ability to interpret their self-reports. Individuals with a BMI below 19 or above 30 will also be excluded, as this would change dosing requirements. Last, for scientific reasons, we will include only individuals who report using marijuana < 100 times in their lifetime, to reduce variation in possible developed tolerance to CBD.

Drug and Doses: We will administer placebo, 300mg, 600mg and 900mg CBD in counterbalanced order under double-blind conditions. Plasma levels peak approximately 1 - 4 hr after oral administration, with mean peak concentration at 90min, and remain elevated up to 12 hr after an acute dose. The 300mg, 600mg and 900mg doses have been effective doses for reducing anxiety in previous studies (Bergamaschi et al. 2011b; Fusar-Poli P and et al. 2009; Zuardi et al. 1993). Using three doses will help establish a dose-response curve for any effects. Doses will be separated by at least 7 days

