Study Session: Please see below for a full timeline of the study session. Participants will be asked to fast overnight. On study session days, participants will arrive at 9am, and consume a standardized snack. Participants will then complete a urine and breath screening for recent alcohol and drug use, and a pregnancy test (for women). We will then take Time 1 measures of subjective mood, drug effects and cardiovascular variables. We will continue to take these same measures periodically throughout the study (see below). Participants will be administered the drug or placebo at 1:30pm. While waiting for the drug effect to reach peak, participants will be allowed to relax and watch a movie or read a book, but will not be allowed to do work. At 2:15 pm, 3 pm, 3:45 pm, we will reassess mood. The task portion of the study will begin approximately 90min after administration of the drug, and will last for approximately 1 hour, to coincide with the peak effect of the drug. The IAPS, DEIT, ABT tasks will be presented in a counterbalanced order. The psychophysiological equipment will then be disconnected and the IST task will be completed. Participants will then remain in the lab completing subjective measures of the drug effect every half-hour until at least 5:45 pm (when we expect drug effects will be decreased sufficiently to permit participants to leave safely), or until drug effects decrease sufficiently to permit participants to leave safely (as measured by both subjective report and cardiovascular variables). Some drug effects may persist for up to 12hrs after the end of the study session, but based on the literature on CBD given chronically to an ambulatory population, these should be mild and non-impairing (Cunha et al. 1980). Sessions will be separated by at least 5 days.

Timeline

1:00pm	- Arrival, snack, breath and urine tests
1:15pm	- Mood (POMS), drug effect (DEQ, ARCI) and cardiovascular measures
1:30pm	- Capsule administered
2:15pm	- Mood (POMS), drug effect (DEQ, ARCI) and cardiovascular measures
3:00pm	- Mood (POMS), drug effect (DEQ, ARCI) and cardiovascular measures
3:45pm	- Mood (POMS), drug effect (DEQ, ARCI) and cardiovascular measures
4:00pm	- IAPS, DEIT, ABT tasks, counterbalanced
4:45pm	- IST task
5:00pm	- Mood (POMS), drug effect (DEQ, ARCI) and cardiovascular measures
5:45pm	- Mood (POMS), drug effect (DEQ, ARCI) and cardiovascular measures
5:50pm	- Leave laboratory

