Debriefing: Participants will return to the lab for a final session at which they will complete a final DEQ rating of how much they liked each study drug and how much they would want to take each study session drug again. Participants will also be asked to report which type or types of drugs they think they received at each session. Finally, participants will be fully debriefed with regard to the study hypotheses, methods and the types of drugs that they received, and will be given a chance to ask any final questions.

Data Analysis

IAPS: We hypothesize that participants will react less to negative pictures while taking CBD, while reactions to positive and neutral slides will be unchanged. We will conduct a Mixed Linear Model analysis in R using lme4 on each dependent variable (subjective ratings, corrugator and startle responses) using Drug (0, 300, 600 and 900mg) and picture type (positive, neutral, negative) as independent variables, and including random variables for Subject and Drug.

DEIT: We hypothesize that participants will show decreased sensitivity to negative facial expressions (anger, sadness and fear) on CBD, as measured by a greater intensity of expression required to identify negative facial expressions, but unchanged intensity for happy facial expressions. We also hypothesize that CBD will reduce negative psychophysiological responses to negative facial expressions, but not happiness. We will conduct a Mixed Linear Model analysis in R using lme4 on each dependent variable (expression intensity and corrugator responses) using Drug (0, 300, 600 and 900mg) and expression type (happy, angry, fearful, sad) as independent variables, and including random variables for Subject, Drug and Actor.

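### Task order is counterbalanced, but the plan does not say whether it is fixed within a participant, and no model includes task position

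*Combined protocol and SAP*

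**What the plan says.** The design is a crossover: "The study will use a 4-session within-subjects double-blind design", with dose order described as "We will administer placebo, 300mg, 600mg and 900mg CBD in counterbalanced order under double-blind conditions". Every dose comparison is therefore made within a person, with one session per dose.

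On task order, the Study Session paragraph says "The IAPS, DEIT, ABT tasks will be presented in a counterbalanced order", and the Timeline repeats it as "IAPS, DEIT, ABT tasks, counterbalanced". Neither place gives the unit of counterbalancing (across participants, or across one participant's sessions) or links task order to dose order. The speech task (IST) always comes last, so its position does not vary.

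Under Data Analysis, the IAPS model is specified "using Drug (0, 300, 600 and 900mg) and picture type (positive, neutral, negative) as independent variables", with random terms for Subject and Drug. The DEIT and ABT models have the same form with expression type in place of picture type, and DEIT also has a random term for Actor. No model contains task position, session number or time since capsule. The IST analysis takes per-participant drug effects on negative stimuli from these models and uses them as mediators.

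On timing, the same section says "Participants will be administered the drug or placebo at 1:30pm" and "The task portion of the study will begin approximately 90min after administration of the drug, and will last for approximately 1 hour", while the Timeline starts the three tasks at 4:00pm.

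**The concern.** Counterbalancing the tasks concedes that position may matter, through fatigue, spill-over from a preceding emotional task, or time since the capsule. The analysis then leaves the factor out.

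Whether that costs anything depends on a detail the plan omits. If each person keeps one order, an additive position effect is the same under every dose and subtracts out of that person's dose contrasts. If order changes from session to session, the same task sits in different positions under different doses. Four sessions cannot balance three positions within one person, so each person's contrasts then carry leftover position differences.

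Three quantities are exposed: Drug main effects; dose contrasts within negative stimuli, which is how the IAPS and DEIT hypotheses are partly worded; and the per-participant drug effects passed to the mediation analysis. Each dose is given in one session only, so a person's drug effect cannot be separated from anything else that differed between sessions. A position difference would be read as an individual drug response.

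**Working it through.** The plan gives no power, alpha, effect size, SD or position effect, so there is no stated figure to reproduce. What follows is a size estimate under stated assumptions.

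**Inputs from the documents.** Four sessions with one dose each; 36 expected completers out of 50 recruited (Subjects); three tasks, hence 3! = 6 orders; capsule at 1:30pm; three-task block from 4:00 to 4:45pm (Timeline).

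**Assumptions.** Within-participant session SD = 1. Position shifts the score by d per step, so positions 1, 2 and 3 contribute -d, 0 and +d. Positions are equally likely, and independent of dose and between sessions. Two-sided alpha is 0.05, and power is 80% without position noise.

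**1. Order fixed within a person.** In a dose-placebo difference the position term is d·p - d·p = 0. The variance ratio is 1.00.

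**2. Order varying by session, position not modelled.** The position variance is (d² + 0 + d²)/3 = 2d²/3 per session. The contrast variance goes from 2/n to 2(1 + 2d²/3)/n, a ratio of 1 + 2d²/3.

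**3. Power.** The starting noncentrality is 1.960 + 0.842 = 2.802. Power becomes Φ(2.802/√ratio - 1.960).

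| d (SD per step) | Variance ratio | Power | Completers lost, 36 × (ratio - 1) |
|---|---|---|---|
| 0.15 | 1.015 | 79.4% | 0.5 |
| 0.30 | 1.060 | 77.7% | 2.2 |
| 0.50 | 1.167 | 73.7% | 6.0 |

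**4. Alternative scheme.** Suppose each task is spread over all three positions within a person, with one position repeated in the four sessions. The mean squared position difference between two sessions is then 5d²/3, so the ratio is 1 + 5d²/6. That gives 1.019, 1.075 and 1.208, with power 79.3%, 77.1% and 72.2%. The table is therefore slightly mild for this scheme.

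**5. Simulation check** (n = 36, d = 0.5, 4,000 runs per case). The SE of the 900 mg-placebo contrast was 0.234 with order fixed, 0.253 with order varying and unadjusted, and 0.237 with order varying and position in the model. Mean bias was about 0 in each case. The Monte Carlo error of each SE is about 0.236/√8000 = 0.003, so the gap at d = 0.5 is real, but this check is too coarse to resolve the smallest position effects.

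**6. What cancels.** Positive and negative stimuli are shown within the same task at the same session. An additive shift d·p is common to both and vanishes from negative minus positive. If position acts on negative stimuli by an extra g per step, g·p remains.

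**7. Time since capsule.** If the three tasks are equal in length (assumed), each takes 45/3 = 15 minutes, and position moves a task by up to 30 minutes. The Timeline start is 150 minutes after the capsule; the text's start of about 90 minutes would be 3:00pm. The stated hour could cover the three tasks plus the IST (4:00 to 5:00pm), so the conflict lies in the start time.

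**The case against.** **Order may already be fixed.** A reader might infer that order does change within a participant. The documents do not say so. One order per person, balanced across people, fits the same words, and the additive loss is then nil. This stands: the finding is an omission in the text together with a missing model term, not a demonstrated design flaw.

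**Not every contrast is affected.** A reader might infer that all IAPS, DEIT and ABT comparisons lose precision. The main hypotheses are selective (negative responses fall, positive ones do not), and an additive shift cancels from those Drug by type contrasts. The ABT pairs an emotional with a neutral face on each trial, and the IAPS EMG has a one-second pre-picture baseline that could remove slow drift. This also stands. The exposure is limited to the three quantities named above, plus any effect of position that differs by stimulus type, which emotional spill-over could produce.

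**Bias.** A reader might infer that dose effects would be biased. Nothing in the documents ties task order to dose, and under independence the expected bias is zero. The plan should nevertheless state that independence.

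**A fixed order is not a complete cure.** A reader might infer that it removes time-since-capsule effects as well. It does not. A pharmacological time course is absent under placebo, so it is a dose-by-time effect and survives in a dose-placebo contrast. With a fixed order it becomes between-person variation in the drug effects used as mediators, and an additive position term does not capture it either. The component may be modest: the Timeline block falls 150 to 195 minutes after the capsule, inside the 1 to 4 hour peak range given under Drug and Doses.

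**The size is assumed.** At the two smaller values the loss is only one to two power points.

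**Conclusion.** The point holds as a low-cost improvement of minor severity. Two gaps are established from the text: the unit of counterbalancing and its independence from dose order are not stated, and no model includes the position factor that the design sets out to balance.

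The consequence is conditional on order varying by session. The cost then runs from negligible (0.15 SD per step) to about six power points, or six of 36 completers' worth of information (0.5 SD per step, which is a full session SD from first to third position). These figures rest on the assumed SD, alpha, baseline power and linear position effect, none of which the documents supply.

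**What to change.** Do one of the following, and state in the Study Session paragraph which applies.

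- **Preferred.** Record the position of each task at each session and add it (1, 2, 3, as a categorical fixed effect) to the IAPS, DEIT and ABT models. The cost is 2 df per model. At d = 0.5 the simulation shows this recovers nearly all the lost precision (SE 0.237 against 0.234 with fixed order).
- **Alternative.** Assign each enrolled participant one of the six task orders, keep it at all four sessions, and allocate it independently of dose order. The cost is one sentence. Allocation is to the 50 recruits (50/6 is not a whole number), so six completers per order (36/6) is a target that dropout may not preserve. Acknowledge that dose-by-time effects remain as between-person variation.

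If order does vary, also state that task order is allocated independently of dose order. If it is already fixed within a person, saying so closes the point.

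Separately, reconcile the task start time in the Study Session text with the Timeline, so that time since capsule is defined. None of this needs extra participants, visits or measurements.

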Program will be used to examine the total number of words as an index of social activity, and the amount of positivity and the amount of negativity expressed in each speech task, as a behavioral index of affect (Pennebaker et al. 2007).

Subjective Measures:

1. Profile of Mood States – POMS (McNair et al. 1971). The POMS is a validated measure consisting of 72 adjectives commonly used to describe momentary mood states. The POMS is highly sensitive to the effects of drugs in similar samples of healthy volunteers (de Wit & Griffiths, 1991; Johanson & Uhlenhuth, 1980), and will be used to assess mood effects of the drug during the study sessions.
2. Drug Effects Questionnaire – DEQ (Fischman and Foltin 1991). The DEQ is a validated measure consisting of questions on a visual analog scale about the subjective effects of drugs. Subjects are asked to rate the extent they feel a drug effect, whether they like or dislike the drug effect, and if given a choice would they want to take more of the drug. This is also be used to assess the pharmacodynamics of the drug effect during the study
3. The Addiction Centre Research Inventory – ARCI (Martin et al. 1971). The ARCI is a true-false questionnaire that consists of empirically derived scales sensitive to the effects of a variety of classes of psychoactive drugs (Haertzen 1966). We used a 53-item version, which yields scores for six scales that include: sedation (Pentobarbital-Chlorpromazine Group; PCAG), stimulant-like effects (Amphetamine; A, and Benzedrine Group; BG), somatic and dysphoric effects (Lysergic Acid; LSD), euphoria (Morphine-Benzedrine Group; MBG), and marijuana-like effects (M).
4. The Evaluative Space Grid – ESG (Larsen et al. 2009). The Evaluative Space Grid is validated measure consisting of a two dimensional grid that provides a single item measure of positivity and negativity. This will be used to measure subjective reactions to the IAPS pictures.

Psychophysiological Measures:

1. Cardiovascular measures – Blood pressure and heart rate will be periodically monitored using portable blood pressure cuffs, to track the cardiovascular effects of the drug, and ensure participant safety.

Procedure:

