ABT: We hypothesize that participants will show reduced attentional bias to negative facial expressions (anger, sadness and fear) on CBD, as measured by increased reaction times for probe response for negative faces, without any change in responses to happy faces. We will conduct a Generalized Mixed Linear Model analysis in R using lme4 on the binomial variable of initial gaze direction with Drug (0, 300, 600 and 900mg) and expression type (happy, angry, fearful, sad) as independent variables, and including random variables for Subject and Drug. We will conduct a Mixed Linear Model analysis in R using lme4 on total dwell time on each face, using Drug (0, 300, 600 and 900mg) and expression type (happy, angry, fearful, sad) as independent variables, and including random variables for Subject and Drug.

IST: We hypothesize that participants will show increased talkativeness on the IST, as measured by total word count and further, that this increased talkativeness will be mediated by reduced negative responses to negative emotional and social cues (as measured in the IAPS, DEIT and ABT). We will first derive per-participant estimates of the effect of drug on responses to negative stimuli from the Mixed Linear Model analyses described above. We will then conduct a Mixed Linear Model analysis in R using lme4 on total word count with Drug (0, 300, 600 and 900mg) as an independent variable, and including random variables for Subject and Drug (per Wardle et al. 2012b). Following criteria for within-subject mediation (Judd et al. 2001), we will first establish whether drug has the hypothesized effect on talkativeness. We will then include the per-participant estimates of the effect of drug on responses to negative stimuli as covariates, and examine 1. Whether changes in responses to negative stimuli account for a significant proportion of changes in talkativeness, and 2. Whether the effect of drug on talkativeness is still significant after inclusion of the changes in responses to negative stimuli. If the effect of drug on effort is wholly mediated by changes in responses to negative stimuli, we would expect the effect of drug on talkativeness to no longer be

significant after including drug-induced changes in responses to negative stimuli as a covariate (see Wardle and de Wit 2012 for an example of this type of analysis).

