Exploratory Analysis of Relationship to Mood: We will conduct similar within-subject mediational Mixed Linear Model analyses in R using lme4 on our primary outcomes of responses to negative stimuli, using subjective measures of anxiety (from the POMS), sedation (from the ARCI) and euphoria (from the POMS, ARCI and DEQ) as covariates. Following the procedure described above, we will determine whether the effects of the drug on responses to negative stimuli are partially or wholly mediated by its effects on subjective mood.

Human Subjects Information

Recruiting methods: We will place print ads in newspapers and on online job search sites such as craigslist.org, and flyer in the Chicago area. Healthy volunteers who respond to our ads are screened using our standard screening protocol for all studies in the Human Behavioral Psychopharmacology Laboratory, which is separately approved by the IRB under Protocol #13681B.

Obtaining consent: Written informed consent for the screening session only is obtained at the screening according to procedures outlined in Protocol #13681B. Written informed consent for the study procedures is obtained at the orientation session, after a verbal explanation of study procedures, check of comprehension, and an opportunity for the participant to ask any questions they may have. Consent is verbally re-verified at the beginning of each study session.

Risk to subjects:

1. Diagnostic procedures and questionnaires: Some of the questions asked during the screening may be considered sensitive information, including drug use history and psychiatric history. We have rigorous procedures in place to ensure confidentiality of data, including locked cabinets for confidential files, subject coding, secure computer systems, and rigorous training of personnel. Please see screening protocol #13681B for full information on steps taken to protect information gathered as part of the screening.

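### Eight outcome models on a four-level Drug factor, with no single or ranked primary outcome for Aims 1 and 2 and no error-rate rule, leave the false-positive rate uncontrolled

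*Combined protocol and SAP*

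**What the plan says.** The Data Analysis section takes the tasks one at a time.

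- **IAPS (Aim 1):** "We will conduct a Mixed Linear Model analysis in R using lme4 on each dependent variable (subjective ratings, corrugator and startle responses", that is, three named outcomes. The ratings come from the Evaluative Space Grid, described under Subjective Measures as "a two dimensional grid that provides a single item measure of positivity and negativity", so they may become two outcomes.
- **DEIT (Aim 2):** a mixed model "on each dependent variable (expression intensity and corrugator responses".
- **ABT (Aim 2):** one model "on the binomial variable of initial gaze direction" and another "on total dwell time on each face". The hypothesis in the same paragraph is worded in terms of probe reaction time, for which no model is given.
- **IST (Aim 3):** one model, on total word count.

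Every model has Drug at 0, 300, 600 and 900 mg. The exploratory mood analysis then speaks of mediation models "on our primary outcomes of responses to negative stimuli", a plural group that is neither listed nor ranked. Study Tasks rules out only DEIT accuracy as a primary variable. The document states no significance level, sidedness, multiplicity adjustment or testing order. It does not name the term that decides a hypothesis (Drug or Drug by stimulus type) or say how the three doses are compared with placebo.

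**The concern.** Aims 1 to 3 carry directional working hypotheses and stand apart from a labelled Exploratory Aim, so they are confirmatory in form. Aim 1 has three or four modelled outcomes and Aim 2 has four. Nothing says whether an aim needs all of its outcomes or any one of them. A report could therefore rest on whichever outcome, dose or model term came out significant and still be consistent with the plan, and a reader could not tell the planned test from the best of several. This matters because the Significance section means to offer a favourable pattern as further evidence for CBD as an anxiety treatment. The IST mediation sequence also begins by asking whether the drug had its predicted effect, without saying which contrast among the four Drug levels answers that.

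**Working it through.** **Inputs from the document.** Outcome models: IAPS 3 + DEIT 2 + ABT 2 + IST 1 = 8. Splitting the ratings gives 9. Leaving out word count, 8 - 1 = 7 concern responses to negative stimuli. Drug has four levels, so there are three dose-versus-placebo comparisons per outcome. Expected completers: 36 of 50 recruited (36/50 = 72%), which is a retention figure and not a power calculation. The plan states no error rate, so there is none to reproduce.

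**Assumed inputs.** Two-sided alpha of 0.05, no CBD effect on any outcome, and a common correlation between outcomes of 0 to 0.7.

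**Step 1: one independent test per outcome, either direction.** The chance of at least one false positive is 1 - 0.95^m.
- m = 7: 30.2%
- m = 8: 33.7%
- m = 9: 37.0%

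**Step 2: the same tests, counted only in the reduced direction.** The chance is 1 - 0.975^m.
- m = 7: 16.2%
- m = 9: 20.4%

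**Step 3: correlation and the four-level factor.** 20,000 simulated null trials per setting, n = 36, four sessions, omnibus repeated-measures F(3,105). Chance (%) of at least one such result:

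| Rule | Outcomes | corr 0 | 0.3 | 0.5 | 0.7 |
|---|---|---|---|---|---|
| Omnibus Drug test significant, either direction | 7 | 30.2 | 27.8 | 23.9 | 19.2 |
| | 9 | 36.9 | 33.3 | 28.0 | 21.8 |
| Omnibus significant and a dose significantly below placebo | 7 | 13.7 | 12.1 | 10.3 | 8.2 |
| | 9 | 17.0 | 14.6 | 12.3 | 9.4 |
| Any dose significantly below placebo, no omnibus gate | 7 | 37.2 | 30.0 | 25.6 | 19.9 |
| | 9 | 45.0 | 35.3 | 29.3 | 22.3 |

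Repeat runs differ by about one percentage point. The nine-outcome rows include word count and positivity ratings, so the seven-outcome rows are the better guide to a claim about negative responses.

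**Step 4: limits of the simulation.** It uses one score per outcome per session and leaves out stimulus type. Free choice between the Drug effect and the Drug by stimulus-type term would raise the figures. Requiring unchanged responses to positive stimuli would lower them.

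**Step 5: power cost of Holm.** For a paired effect of 0.48 SD with n = 36, power is 0.80 at alpha 0.05. At the first Holm step among three outcomes, 0.05/3 = 0.0167, it is 0.64.

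**Step 6: why the p-value method should be stated.** If Drug effects vary by participant and a 3-df chi-square cut-off of 7.815 were used, the actual size at n = 36 would be P(F(3,33) > 7.815 x 33/105 = 2.456) = 0.080, not 0.05. The plan does not say that it will use this test. It names no test at all.

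**The case against.** A reader might infer that a false finding that CBD reduced a negative response is more likely than one in four. The documents do not support that without conditions. The 30-37% figures count either direction. For a reduction, one directional test per outcome gives 16-20% for seven to nine outcomes, and gating by the omnibus test gives at most 17%. One in four is passed only if doses are compared directly with placebo and the correlation is at most about 0.5. The plan mentions no pairwise dose tests, and Drug and Doses gives the purpose of three doses as a dose-response curve. A count of 9 x 3 = 27 planned tests is therefore not in the text either.

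It would also be too strong to say that there is no primary outcome. The negative-stimulus responses are called primary as a group, and Aim 3 has word count.

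The hypotheses are worded jointly. Aim 1 speaks of subjective and psychophysiological responses, Aim 2 lists three effects, and both expect positive responses to be unchanged. The treatment inference under Significance further asks for a link to social behaviour. One stray p-value would not fit that wording.

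These points narrow the size of the problem and stand to that extent. None of them is a decision rule: the plan does not say that an aim fails if one of its outcomes fails, and it contains no omnibus gate. The favourable figures depend on rules that it does not state.

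**Conclusion.** The concern holds in a limited form. For Aims 1 and 2 the plan has an unranked set of primary outcomes, and for all three aims it lacks a deciding contrast, a dose-comparison rule and error control. Under the stated assumptions (two-sided 5%, n = 36, no effect, correlation 0 to 0.7), the chance of some significant omnibus result in either direction is about 19-30% for seven outcomes and 22-37% for nine. The chance of a false reduction runs from about 8% (gated, seven outcomes, correlation 0.7) to about 45% (direct comparisons, nine outcomes, correlation 0). The width of that range is itself the finding, because it depends largely on rules the plan leaves open. The correlations and alpha are assumptions, not figures from the document. This should be corrected, but it does not invalidate the design.

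**What to change.** In the Data Analysis section:

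- Name one primary outcome for Aim 1 and one for Aim 2 (the sponsor's choice), and keep word count for Aim 3.
- Name one planned Drug contrast per aim, tested at two-sided 5%. For Aims 1 and 2 it should be on the response to negative stimuli or on the Drug by stimulus-type term.
- Apply Holm to the remaining outcomes within Aim 1 and within Aim 2.
- Adjust the three dose-versus-placebo comparisons by Dunnett or Holm.
- State that a secondary outcome alone does not support an aim.
- State how p-values are obtained: Kenward-Roger F tests for the linear mixed models only, and a likelihood-ratio or parametric-bootstrap test for the binomial initial-gaze model.

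This is wording only, with no added participants, sessions or measurements. Secondary outcomes lose some power: about 80% falls to 64% at the first Holm step among three. Error is then controlled within each aim, not across them. Three independent primary tests at 5% still give 1 - 0.95^3 = 14.3% for any false positive. That is acceptable if the aims are reported as separate questions, and the plan should say so.
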